2.14 Interim analysis

No interim analysis is planned for this study.

3 Sample size calculation

To assess the assumed effect size at Week 8, a 43.6% response rate (spinal pain NRS < 4) is assumed for the secukinumab 150 mg group. This number is derived as an average of the response rates observed in the CAIN457F2320 and CAIN457F2310 studies ([Baeten et al 2015](#)). For the placebo group, a response rate at Week 8 of 23.5% (NRS < 4) was selected as assessed in the CAIN457F2320 study. This intermediate scenario takes into consideration a certain likelihood of a relatively high placebo response also in line with data from the TNF α reference studies and the CAIN457F2305 study in addition to the slightly milder course of the disease in the studied population ([Baeten et al 2015](#)).

Assuming conservatively a response rate of 23.5% in the placebo group and a response rate of 43.6% under secukinumab 150 mg, 332 patients in total (i.e. 249 patients in secukinumab 150 mg group and 83 patients in placebo group) would be needed under 3:1 (secukinumab: placebo) allocation to achieve 90% power on a (2-sided) 5% significance level. To compensate for drop-out patients or those with protocol deviations, a total of 352 patients (264 in secukinumab 150 mg group and 88 in the placebo group) should be recruited.

4 Change to protocol specified analyses

None.

5 Appendix

5.1 Imputation rules

5.1.1 Study drug

Not Applicable

5.1.2 AE date imputation

AE date imputation is based only on a comparison of the partial AE start date to the treatment start date as mentioned in the Table 1-2 below.

1. If the AE start date year value is missing, the date uncertainty is too high to impute a rational date. Therefore, if the AE year value is missing, the imputed AE start date is set to NULL.
2. If the AE start date year value is less than the treatment start date year value, the AE started before treatment. Therefore:
 - a. If the AE year is less than the treatment year and the AE month is missing, the imputed AE start date is set to the mid-year point (01JulYYYY).
 - b. Else if the AE year is less than the treatment year and the AE month is not missing, the imputed AE start date is set to the mid-month point (15MONYYYY).
3. If the AE start date year value is greater than the treatment start date year value, the AE started after treatment. Therefore:
 - a. If the AE year is greater than the treatment year and the AE month is missing, the imputed AE start date is set to the year start point (01JanYYYY).
 - b. Else if the AE year is greater than the treatment year and the AE month is not missing, the imputed AE start date is set to the month start point (01MONYYYY).
4. If the AE start date year value is equal to the treatment start date year value:
 - a. And the AE month is missing or the AE month is equal to the treatment start month, the imputed AE start date is set to one day after treatment start.
 - b. Else if the AE month is less than the treatment start month, the imputed AE start date is set to the mid-month point (15MONYYYY).
 - c. Else if the AE month is greater than the treatment start month, the imputed AE start date is set to the start month point (01MONYYYY).

Table 5.1-2: AE start date imputation

	MON	MON < CFM	MON = CFM	MON > CFM
	MISSING			
YYYY MISSING	NULL	NULL	NULL	NULL
	Uncertain	Uncertain	Uncertain	Uncertain
YYYY < CFY	(D) = 01JULYYYY	(C)= 15MONYYYY	(C)= 15MONYYYY	(C)= 15MONYYYY
	Before Treatment Start	Before Treatment Start	Before Treatment Start	Before Treatment Start
YYYY = CFY	(B)= TRTSTD+1	(C)= 15MONYYYY	(A)= TRTSTD+1	(A)= 01MONYYYY
	Uncertain	Before Treatment Start	Uncertain	After Treatment Start
YYYY > CFY	(E)= 01JANYYYY	(A)= 01MONYYYY	(A)= 01MONYYYY	(A)= 01MONYYYY
	After Treatment Start	After Treatment Start	After Treatment Start	After Treatment Start
Before Treatment Start	Partial indicates date prior to Treatment Start Date			
After Treatment Start	Partial indicates date after Treatment Start Date			
Uncertain	Partial insufficient to determine relationship to Treatment Start Date			
LEGEND:				

(A)	MAX(01MONYYYY,TRTSTD+1)
(B)	TRTSTD+1
(C)	15MONYYYY
(D)	01JULYYYY
(E)	01JANYYYY

AE end date imputation

For the purpose of date imputation, the study treatment follow-up period date is defined as the last available visit date, i.e. including unscheduled visits after the end of study visit.

1. If the AE end date month is missing, the imputed end date should be set to the earliest of the (study treatment follow-up period date, 31DECYYYY, date of death).
2. If the AE end date day is missing, the imputed end date should be set to the earliest of the (study treatment follow-up period date, last day of the month, date of death).
3. If AE year is missing or AE is ongoing, the end date will not be imputed.

If the imputed AE end date is less than the existing AE start date then use AE start date as AE end date.

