## 6.1 Information to be collected on screening failures

All patients who have signed informed consent but not entered into the next period will have the study completion page for the Screening period, demographics, inclusion/exclusion, and SAE data collected. Adverse events that are not SAEs will be followed by the investigator and collected only in the source data. Information on withdrawal of consent must be completed if consent has been withdrawn during the Screening period. The Death eCRF should be completed in the case of death during the Screening period.

All patients who provide signed informed consent but discontinue prior to first intake of study drug on Day 1 (Baseline Visit) are considered to be screen failures. If a patient discontinues prior to or at Day 1, the reason for screen failure will be entered on the appropriate eCRF page. For details on completing the eCRF please refer to the CRF completion guideline.

For all patients who sign the informed consent and enter into the next period of the study, all AEs occurring after the informed consent is signed will be recorded on the AE eCRF page.

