2.1.1 General definitions

Study treatment: Study treatment refers to:

Secukinumab 150 mg provided in 1 ml PFS or secukinumab placebo provided in 1 ml PFS.

Study treatment start and end date: Study treatment start date is defined as the first date, when a non-zero dose of study drug is administered and recorded on the Drug Administration Record (DAR) CRF page. Similarly, study drug end date is defined as the last date, when a non-zero dose of study drug is administered and recorded on the DAR CRF page of the core study.

Study day: Study day will be calculated as (event date – study drug start date + 1 day) for events that occurred on or after study drug start date (e.g., visit, lab samples, AEs). For events prior to study drug start date (e.g., time of diagnosis), study day will be negative and calculated as (event date – study drug start date). Note that study drug start date is study day 1 and the day before study drug start date is study day -1 (i.e. no study day 0).

Due to the study drug dosing schedule, one month will be considered as 28 days. However, for “time since event” data (e.g., medical history), one month will be considered as 365.25/12 days for events that occurred prior to study Day 1. Time from events prior to the start of study drug, e.g., time since diagnosis, is calculated as the difference between the start date of study drug and the date of prior event.

Note that, the first dose day is Day 1, and the day before the first dose day is counted as Day - 1 (not Day 0).

Baseline and post baseline: In general, a *baseline* value refers to the last measurement made prior to administration of the first dose of study treatment. A post-baseline value refers to a measurement taken after the first dose of study treatment.

Treatment Period: There are 2 treatment periods for this study defined as:

Treatment Period 1 is defined as an 8-week placebo-controlled, double-blind treatment period starting from baseline till Week 8. Assessments of Week 8 are included in TP1 whereas administration of study drug at week 8 will be a part of TP2. Week 8 is the last visit of TP1 for all assessments except drug intake.

Treatment Period 2 is a 16 week double-blinded, active treatment period starting from Week 8 till Week 24 for administration of study drug. Week 8 assessments are considered as the baseline values for assessments during TP2.

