2.8.1 Adverse events (AEs)

Summary tables for adverse events (AEs) will include only the **treatment-emergent** AEs i.e. events that started after the first dose of study treatment or events present prior to the first dose of study treatment but increased in severity based on preferred term until 12 weeks after last dose of study treatment.

The treatment-emergent adverse events will be summarized by system organ class and preferred term, severity (mild, moderate, severe), type of adverse event, relation to study treatment. If a patient reported more than one AE with the same preferred term, the AE with the greatest severity will be presented. If a patient reported more than one AE within the same primary system organ class, the patient will be counted only once with the greatest severity at the system organ class level, where applicable.

For the reporting requirements of ClinicalTrials.gov and EudraCT, two required tables on <on-treatment/treatment emergent> adverse events which are not serious adverse events with an incidence greater than 2% and on <on-treatment/treatment emergent> SAEs and SAEs suspected to be related to study treatment will be provided by SOC system organ class and PT preferred term on the safety set population.

If for a same patient, several consecutive AEs (irrespective of study treatment causality, seriousness and severity) occurred with the same SOC and PT:

- a single occurrence will be counted if there is ≤ 1 day gap between the end date of the preceding AE and the start date of the consecutive AE
- more than one occurrence will be counted if there is > 1 day gap between the end date of the preceding AE and the start date of the consecutive AE

For calculating the frequencies, the presence of at least one SAE / SAE suspected to be related to study treatment / non SAE has to be checked in a block e.g., among AE's in a ≤ 1 day gap block, if at least one SAE is occurring, then one occurrence is calculated for that SAE.

The following adverse event summaries will be produced by treatment for Safety Set:

- Adverse events (overall and severe), regardless of study drug relationship by primary system organ class and preferred term
- Adverse events, regardless of study drug relationship by primary system organ class and preferred term and severity
- Adverse events (overall and severe), with suspected study drug relationship by primary system organ class and by preferred term

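### SAP 5.1.2 ignores the AE end date when it imputes a partial start date, so some screening events that ended before the first dose are dated to Day 2 and counted as treatment-emergent (minor safety impact)

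*SAP*

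**What the plan says.** **Start-date rule.** SAP 5.1.2 opens by saying that "AE date imputation is based only on a comparison of the partial AE start date to the treatment start date". In rule 4a, when the year equals the treatment start year and the month is missing or equals the treatment start month, "the imputed AE start date is set to one day after treatment start". SAP 2.1.1 numbers the first dose as Day 1 ("Note that study drug start date is study day 1"), so this is Day 2. Table 5.1-2 labels these cells Uncertain, which its key explains as "Partial insufficient to determine relationship to Treatment Start Date".

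**Other cells.** Rule 4b reads "Else if the AE month is less than the treatment start month, the imputed AE start date is set to the mid-month point", and rule 2 likewise places earlier-year dates in the earlier year. Both results fall before treatment. A missing year is left null.

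**Consistency check.** The end-date part of SAP 5.1.2 has one: "If the imputed AE end date is less than the existing AE start date then use AE start date as AE end date".

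**Use of the date.** SAP 2.8.1 counts as treatment-emergent "events that started after the first dose of study treatment", plus earlier events that worsened. It sets no condition on the end date.

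**Data available.** For patients who go on past screening, Protocol 6.1 says that "all AEs occurring after the informed consent is signed will be recorded on the AE eCRF page". Protocol 7.1 collects both start and end dates, and Protocol 3.1 allows up to 10 weeks of screening.

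**The concern.** Dating an event to just after the first dose is a sensible cautious default when nobody knows whether it began before or after. A recorded end date before the first dose removes that doubt, because the event was over before any drug was given. Rule 4a cannot use this information.

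The result is an impossible record, with its start after its end, and an event that preceded treatment is reported as arising on treatment. Crude treatment-emergent rates, the AE tables built on them and the exposure-adjusted rates are at stake. Data-entry checks (Protocol 8.2) would not reveal it: a start of March with the day unknown and an end of 10 March agree with each other. The imputation creates the conflict.

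**Working it through.** The documents give no figure to reproduce. The check applies the date rules to an assumed first dose of 20 March 2018.

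**Step 1: apply rules 1 to 4.** Programmed, they agree with every cell of Table 5.1-2.

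| Recorded start | Recorded end | Imputed start | Classified as |
|---|---|---|---|
| March 2018, day missing | 10 March 2018 | 21 March 2018 (Day 2) | treatment-emergent, wrong |
| 2018, month missing | 25 February 2018 | 21 March 2018 (Day 2) | treatment-emergent, wrong |
| March 2018, day missing | 28 March 2018 or ongoing | 21 March 2018 (Day 2) | treatment-emergent, reasonable default |
| February 2018, day missing | any | 15 February 2018 | before treatment |
| 2017, month missing | any | 1 July 2017 | before treatment |

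In the first row the imputed start falls 21 − 10 = 11 days after the event ended.

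**Step 2: apply the consistency check.** It acts only on an imputed end date, so the complete end dates in rows 1 and 2 are untouched. With a partial end date (start 2018, end February 2018), the end is imputed as 28 February. If the existing start date is read to include an imputed one, the end is then moved to 21 March and the contradiction disappears from view.

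**Step 3: how many screening onsets go to Day 2.** This assumes onset uniform over screening and first-dose dates uniform over a calendar year. The share is the number of screening days in the first-dose month (day missing) or first-dose year (month missing), divided by all screening days.

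| Screening length | Day missing | Month also missing |
|---|---|---|
| 28 days | 52% | 96% |
| 70 days | 21% | 90% |

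These are shares of screening AEs with a partial start date, not of all AEs. They include events still ongoing at first dose, for which Day 2 is a fair default, so they are upper bounds on misclassification.

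**Step 4: require the event to have ended before the first dose.** The documents give no AE durations. As an illustration, take exponential durations with mean 7 or 14 days. An event starting g days before the first dose is then over by that date with probability 1 − exp(−g/mean).

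| Screening length | Day missing (mean 7, mean 14) | Month also missing (mean 7, mean 14) |
|---|---|---|
| 28 days | 34.7%, 24.5% | 73.6%, 55.5% |
| 70 days | 14.0%, 9.9% | 81.2%, 71.8% |

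**Step 5: exposure-adjusted rates (SAP 2.8.1).** Time to an event is the AE start date minus the reference dose date, plus 1.
- Treatment Period 1 reports, both groups: 2 − 1 + 1 = 2 days.
- Entire period, Group A: the first active dose is Day 1, so again 2 days.
- Entire period, Group B: time runs from the first active dose, scheduled for Day 57 (SAP Table 2-1). This gives 2 − 57 + 1 = −54 days. The event precedes the first active dose, and the formula does not say what to do with it.

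**The case against.** Treating uncertain timing as treatment-emergent is a deliberate safety convention. It over-counts events and hides no harm. Five conditions must also hold together: onset after consent, a partial start date, a start year equal to the first-dose year, a month that is missing or equal to the first-dose month, and an end date known to precede the first dose. AEs are sought at every visit (Protocol 7.1) and entered data are queried for completeness (Protocol 8.3), so few records should qualify.

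The points on scope and likely frequency stand, and they keep the impact minor. The appeal to convention does not cover these cases, because the recorded end date settles what the partial start leaves open. For concomitant medication in the same cells, SAP 5.1.3 does use further information, namely a timing flag.

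Four stronger readings are tempting, but the documents do not support them:
- **All partially dated screening events that ended early move to Day 2.** Rules 2 and 4b already place earlier-month and earlier-year dates before treatment.
- **The 52%, 21%, 96% and 90% shares measure misclassification.** They ignore the end date.
- **Every such event carries 2 days at risk.** This fails for Group B in the entire-period formula.
- **The comparison of active with placebo is materially distorted.** Equal false counts in both arms would pull it toward no difference, but nothing in the documents gives the size.

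**Conclusion.** The rule is wrong as written for a narrow set of records: partial start dates in the first-dose year, with the month missing or equal to the first-dose month, and a recorded end before the first dose. For these it produces a start after the end and a false treatment-emergent event, and no other AE rule corrects it.

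The effect is to inflate crude treatment-emergent rates in both arms, with the uneven handling in the exposure-adjusted rates shown above. The absolute number of events cannot be derived, because the documents do not say how often AE start dates are partial; it is probably small. The percentages rest on the uniformity assumptions and, where the end date is taken into account, on assumed durations. The primary and secondary efficacy analyses are not touched. The case for changing the rule is that the error is certain where it applies and cheap to remove.

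**What to change.** Add to SAP 5.1.2, for the cells that receive treatment start + 1 only:

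- (a) If the AE end date is complete and earlier than treatment start + 1, set the imputed start date to the end date.
- (b) If the end date is partial and its latest possible date (last day of the stated month or year) is before the first dose, set the imputed start date to that latest possible date.
- (c) Otherwise (end on or after treatment start + 1, ongoing, or not determinable), keep treatment start + 1.

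Apply this before the end-date consistency check, and state that the existing AE start date in that check means the start date after this step. The three cases do not overlap; an end date on Day 1 falls under (a).

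In the worked example, the first row becomes 10 March and the second 25 February, neither of them treatment-emergent. The third row stays at 21 March, so the cautious default is kept where timing is truly unknown. The cost is a short SAP addition and minor programming, with no new data and no change to the other cells.

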5.1.3 Concomitant medication date imputation

Concomitant medication (CMD) date imputation uses both a comparison of the partial CMD start date to the treatment start date, and the value of the CMDTYP1C flag (1, 2, or 3). Event date comparisons to treatment start date are made based on the year and month values only (any day values are ignored) in Table 1-3 below.

1. If the CMD start date year value is missing, the date will be imputed based on the CMDTYP1C flag value. If the flag value is 1 or 3, the imputed CMD start date is set to one day before the treatment start date. Else, if the flag value is missing or 2, the imputed CMD start date is set to one day after the treatment start date. (Note that for some legacy data, the CMDTYP1C variable may not exist in the data. When this happens and the CMD start date year value is missing, the imputed date value will be NULL.)
2. If the CMD start date year value is less than the treatment start date year value, the CMD started before treatment. Therefore:
 - a. if the CMD year is less than the treatment year and the CMD month is missing, the imputed CMD start date is set to the mid-year point (01JulYYYY).
 - b. Else if the CMD year is less than the treatment year and the CMD month is not missing, the imputed CMD start date is set to the mid-month point (15MONYYYY).
3. If the CMD start date year value is greater than the treatment start date year value, the CMD started after treatment. Therefore:
 - a. If the CMD year is greater than the treatment year and the CMD month is missing, the imputed CMD start date is set to the year start point (01JanYYYY).

- b. Else if the CMD year is greater than the treatment year and the CMD month is not missing, the imputed CMD start date is set to the month start point (01MONYYYY).

4. If the CMD start date year value is equal to the treatment start date year value:

- a. and the CMD month is missing or the CMD month is equal to the treatment start month,
 - i. If the flag value is 1 or 3, the imputed CMD start date is set to one day before the treatment start date.
 - ii. Else, if the flag value is missing or 2, the imputed CMD start date is set to one day after the treatment start date.
- b. Else if the CMD month is less than the treatment start month, the imputed CMD start date is set to the mid-month point (15MONYYYY).
- c. Else if the CMD month is greater than the treatment start month, the imputed CMD start date is set to the start month point (01MONYYYY).

Table 5.1-3: CMD date imputation

	MON MISSING	MON < CFM	MON = CFM	MON > CFM
YYYY MISSING	(F)	(F)	(F)	(F)
	Uncertain	Uncertain	Uncertain	Uncertain
YYYY < CFY	(D)=01JULYYYY	(C)=15MONYY	(C)=15MONYY	(C)=15MONYY
	Before Treatment Start	Before Treatment Start	Before Treatment Start	Before Treatment Start
YYYY = CFY	(B)	(C)=15MONYY	(B)	(A)=01MONYYYY
	Uncertain	Before Treatment Start	Uncertain	After Treatment Start
YYYY > CFY	(E)= 01JANYYYY	(A)=01MONYYYY	(A)=01MONYYYY	(A)=01MONYYYY
	After Treatment Start	After Treatment Start	After Treatment Start	After Treatment Start
<hr/>				
Before Treatment Start	Partial indicates date prior to Treatment Start Date			
After Treatment Start	Partial indicates date after Treatment Start Date			
Uncertain	Partial insufficient to determine relationship to Treatment Start Date			
LEGEND:				
(A)	MAX (01MONYYYY,TRTSTD+1)			
(B)	IF CMDTYP1C IN (1,3) THEN TRTSTD-1 ELSE IF CMDTYP1C in (., 2) THEN TRTSTD+1			
(C)	15MONYYYY			
(D)	01JULYYYY			
(E)	01JANYYYY			
(F)	IF CMDTYP1C IN (1,3) THEN TRTSTD-1 ELSE IF CMDTYP1C in (., 2) THEN TRTSTD+1			

CM end date imputation

1. If the CM end date year value is missing, the date uncertainty is too high to impute a rational date. Therefore, if the CM end year value is missing or ongoing, the imputed CM end date will be set to NULL.
2. Else, if the CM end date month is missing, the imputed end date will be set to the earliest of the (Last contact date of subject in study, 31DECYYYY, date of death).
3. If the CM end date day is missing, the imputed end date will be set to the earliest of the (Last contact date of subject in study, last day of the month, date of death).
4. If the imputed CM end date is less than the existing CM start date, the CM start date will be used as the imputed CM end date.

5.1.3.1 Prior therapies date imputation

Not applicable

